### 6.1.1.2 Sensitivity analyses

To assess sensitivity of the results, the primary analyses will be repeated for:

- PP population with observed cases,
- ITT with observed cases, and
- ITT with missing value treated as no eyebrow lift (worst case analysis).

Observed cases are those not missing on primary analysis (section 6.1.1.1).

[figure not shown]
Additionally, further sensitivity analyses will be performed with regard to image quality as assessed by the central photography vendor. The following analyses will be performed, treating assessments that are based on photographs with not approved image quality as missing:

- PP population with observed cases,
- ITT with observed cases, and
- ITT with missing values imputed by multiple imputation.

For the sensitivity analysis using multiple imputation approach, similar methods as described in section 6.1.1.1 will be performed.

For all other sensitivity analyses, results can be taken directly from the SAS proc freq output:

CCI

, where response\_data is the dataset with overall lift data per subject. The point estimate for the proportion of responders and the lower limit of the one-sided 95% Wilson CI will be used to assess sensitivity.

A sensitivity analysis will not be done, if identical to any other analysis.

### 6.1.1.3 Subgroup analyses

Gain or loss of  $\geq 2$  BMI units from screening to Day 90 will be considered a major protocol deviation. Subjects with gain or loss of  $\geq 2$  BMI units from screening to Day 90 will be excluded from PP population. The following subgroups will be defined by the change in body weight from screening to Day 90:

- Subjects in ITT population with gain of  $\geq 2$  BMI units;
- Subjects in ITT population with loss of  $\geq 2$  BMI units; and
- Subjects in ITT population with change of  $< 2$  BMI units.

Primary endpoint with observed cases will be analyzed in all subgroups, as defined above, with more than five subjects.

Frequency tables for the proportion of treated subjects with eyebrow lift (primary endpoint) will be provided by age categories ( $\leq$  median age,  $>$  median age), BMI at baseline in categories ( $<18.5$ ,  $18.5 - 24.9$ ,  $25 - 29.9$ ,  $\geq 30.0$ ) and by investigational site.

### 6.1.2 Secondary Effectiveness Endpoints

#### Independent Photographic Review for Eyebrow Lift at Day 180

The secondary endpoint will only be assessed among Stage 1 subjects who reconsented for extended study participation and all Stage 2 subjects.

The secondary endpoint of the study is the proportion of treated subjects with eyebrow lift by comparing photographs taken at Day 180 (post-treatment) with baseline (pre-treatment) photographs.

Each independent evaluator will assess “Eyebrow Lift”, “No Eyebrow Lift” or “Cannot Evaluate” between Photograph 1 (baseline) and Photograph 2 (post-baseline). Photograph 1 will be identified, and the independent evaluators will be blinded to the random distribution of treated versus untreated status of the comparator Photograph 2 (i.e., Day 180 post-treatment among treated subjects or post-baseline for untreated individuals). Lift will be declared if at least two blinded evaluators indicate “Eyebrow Lift” for the comparator photograph. In case at least two evaluators declare a photograph as not assessable (i.e., “Cannot Evaluate” is ticked), the corresponding lift score over all evaluators will be set to missing for the secondary analysis.

The point estimate for the proportion of subjects fulfilling the qualitative eyebrow lift will be described by frequency statistics for the ITT subset, including the one-sided 95% Wilson CI.

Missing data, including a missing secondary endpoint assessment in subjects with unacceptable or missing photographs at baseline or Day 180, will be imputed by multiple imputation 50 times. Imputation is done using a fully conditional specification logistic regression method, as implemented in SAS PROC MI with statement FCS LOGISTIC, and will use the investigational site and the baseline characteristics age and BMI as informing variables. Point estimate and Wilson CI will be calculated with methods as described in Section 6.1.1.1. For implementation, SAS code similar to the statements for the primary endpoint will be used.

Sensitivity analyses and subgroup analyses will be performed similar to the primary endpoint.

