11 STUDY PROCEDURES

11.1 Visit Schedule

The investigation activities and visit schedule are detailed in the Schedule of Events
CCI [REDACTED]

The purpose of the screening visit (Visit 1) is to determine subject eligibility for study participation and must be completed no more than 21 days prior to Day 1 (Visit 2). Informed consent is to be obtained at the screening visit, and the reviewing/recording of AEs begins upon ICF signature. Subject demographics, including FST CCI [REDACTED] should be recorded in the eCRF, and a subject-reported medical history is acceptable.

Note: Additionally, for each site, approximately the first four to five subjects with mild to moderate brow and upper face laxity, as well as mid- to lower face and/or submental fine lines, wrinkles, and laxity, as enrolled by the investigator, will be confirmed for study-appropriate findings via an independent photographic reviewer.

In addition to the activities listed in the Schedule of Events CCI [REDACTED]

- At Visit 2 (Day 1), prior to performing the investigator's skin examination, the subject must wash the treatment area to remove any moisturizers/emoilients, makeup, bronzing agents, etc. on the face and/or neck region, if necessary.
- CCI [REDACTED]
- At Visit 3, Stage 1 subjects will be requested to reconsent for extended study participation to 180 days. If reconsented, study personnel should schedule follow-up Day 120 and Day 150 phone call(s) and Visit 4.
- All required subject-related, pre-treatment procedures and assessments should be completed before the administration of oral or IM pain medication ([Section 10.5.1.2](#)).
- After administration of the pain medication, study personnel should verify all study-specific treatment settings on the Octave System and prepare study-specific materials needed for treatment (e.g., ultrasound gel). Study personnel should prepare inhaled nitrous oxide/oxygen mixture for potential use, if available.

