11.2.1.1 Standardized 2D Photographs

For assessment of the primary effectiveness endpoint, standardized 2D photographs will be taken at the screening visit and at Day 90, at a minimum. Among reconsented Stage 1 subjects and all Stage 2 subjects, additional standardized 2D photographs will be taken at Day 180. Frontal and oblique views of the face and neck are to be obtained using the camera system provided, paired with the Canfield IntelliStudio platform to standardize image capture. Standardized 2D photographs will be utilized to complete the independent photographic review ([Section 11.2.1.1.2](#)), the quantitative eyebrow lift measurement ([Section 11.2.1.2.1](#)), and the quantitative assessment of the forehead and jawline ([Section 11.2.1.2.2](#)).

Since photographs are of critical importance as a reference measure throughout the study, the 2D photographs taken at the screening visit (Visit 1) will be reviewed and accepted by the central photography vendor prior to treatment. If a subject's screening photographs are deemed unsatisfactory by the central photography vendor, photographs will be retaken at Visit 2. Any additional photographs collected at Visit 2 must be collected prior to treatment administration. If repeat photography is needed, the Visit 2 (pre-treatment) photographs will default to the baseline photographs and will be used for reference throughout the study. If no repeat photography is needed, the screening photographs will default to the baseline (pre-treatment) photographs and will be used for reference throughout the study.

At each site, the respective study photographers must be trained in taking standardized photographs and follow the instructions provided in a separate photography user manual. It is of the utmost importance that subjects are photographed in highly standardized positions and with the same setup (i.e., standardized distance, area, views, color standard, lighting, and background). Every effort should be made to have the same trained study personnel take photographs at every visit, and to maintain the setup of the photo studio over the course of the study, with the identical and exact fixed camera positions for the different views and light setups.

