evaluators. Using this 2:1 ratio of treated subjects to untreated individuals, image sets of these untreated individuals will be randomly distributed among the pre- and post-treatment image sets of the treated subjects and presented to the blinded evaluators. For the primary effectiveness endpoint, the “baseline” photograph will be identified as “Photograph 1”, and the independent evaluators will be blinded to the randomly distributed treated versus untreated status of the comparator Photograph 2 (i.e., Day 90 post-treatment among treated subjects or post-baseline for untreated individuals). The same photographic assessment will be used for the secondary effectiveness endpoint with the comparator Photograph 2 collected at Day 180 post-treatment.

Study subjects will have approximately 4 on-site study visits, including screening, baseline/treatment, a Day 90 ( $\pm$  7 days) post-treatment visit, and a Day 180 ( $\pm$  14 days) post-treatment visit. Follow-up telephone calls (TCs) will occur at 3 days ( $\pm$  1 day), 14 days ( $\pm$  3 days), 28 days (+ 3 days), 120 days ( $\pm$  7 days), and 150 days ( $\pm$  7 days) after Octave-Ultherapy treatment. The primary effectiveness endpoint, the proportion of treated subjects with eyebrow lift, will be evaluated using a blinded, independent assessment of photographs at post-treatment Day 90 compared to baseline. Lift is concluded if at least two of three independent, blinded evaluators report “eyebrow lift” in the Day 90 standardized, photographic images when compared to baseline photographic images.

Secondary effectiveness evaluations will include a qualitative assessment of improvement in eyebrow lift at Day 180, as well as Day 90 and Day 180 evaluations of quantitative measurement of eyebrow lift and change from baseline in three FACE-Q modules (i.e., Satisfaction with Forehead and Eyebrows, Satisfaction with Lower Face and Jawline, and Patient-perceived Age visual analogue scale (VAS)).

Standard safety evaluations, including the incidence of adverse events (AEs) and serious adverse events (SAEs), will be assessed.

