In a first step a total of  $m=50$  imputed datasets will be generated, where missing data in the primary endpoint (lift over all evaluators) is modelled via logistic regression based on input variables site, age and BMI at baseline. 

  response is coded as ("no lift", "lift"). The lower bound of the one-sided 95% Wilson CI ([WL, WU]) will be calculated using the following steps, as detailed in [1]:

1. The mean sample response  $\hat{p}_{Imp}$  and sample variance  $\hat{U}_{Imp}$ ,

$$\hat{U}_{Imp} = \frac{\hat{p}_{Imp} (1 - \hat{p}_{Imp})}{n},$$

will be calculated for each of the  $m=50$  imputed datasets with sample size  $n$ .

2. The overall mean  $\bar{p}_m$  and variance  $\bar{U}_m$  over all imputed datasets will be calculated:

$$\bar{p}_m = \frac{1}{m} \sum_{Imp=1}^m \hat{p}_{Imp},$$

$$\bar{U}_m = \frac{1}{m} \sum_{Imp=1}^m \hat{U}_{Imp}.$$

These will be used to obtain  $B_m$ ,

$$B_m = \frac{1}{m-1} \sum_{Imp=1}^m (\hat{p}_{Imp} - \bar{p}_m)^2,$$

the between-sample variance.

3. The lower boundary of the one-sided 95% Wilson CI (WL and WU) will be calculated as

$$\left[ \frac{2\bar{p}_m + \frac{t^2}{n} + \frac{t^2 r_m}{n}}{2 \left( 1 + \frac{t^2}{n} + \frac{t^2 r_m}{n} \right)} - \sqrt{\frac{\left( 2\bar{p}_m + \frac{t^2}{n} + \frac{t^2 r_m}{n} \right)^2}{4 \left( 1 + \frac{t^2}{n} + \frac{t^2 r_m}{n} \right)^2} - \frac{\bar{p}_m^2}{1 + \frac{t^2}{n} + \frac{t^2 r_m}{n}}} \right],$$

where  $t$  denotes the 0.95 quantile of the t-distribution with degrees of freedom  $\nu$ ,

$$\nu = (m - 1) \left( 1 + \frac{1}{r_m} \right),$$

and with

$$r_m = \left( 1 + \frac{1}{m} \right) \frac{B_m}{U_m}.$$

The study is considered successful, and consequently effectiveness is established, if the parameter estimate  $\bar{p}_m \geq 65\%$  (condition A), and the lower limit of the one-sided 95% Wilson CI exceeds the margin of 50% (condition B).

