## **6.4 Special Statistical/Analytical Issues**

### **6.4.1 Discontinuations and Missing Data**

#### **Independent Photographic Review for Eyebrow Lift at Day 90 and Day 180**

For analysis of the primary and secondary effectiveness endpoints regarding Independent Photographic Review for Eyebrow lift, the following procedure for incomplete data from the independent evaluators will be applied:

[figure not shown]
- If data from all three independent evaluators is missing, the outcome of the subject will be set to missing.
- If the result of two out of three evaluators is missing, the outcome of the subject will be set to missing.

- If the result of one evaluator is missing and the other two evaluators agree on the assessment “Eyebrow Lift” then the outcome of the subject is set to “lift” for all analyses.
- If the result of one evaluator is missing and the other two evaluators agree on the assessment “No Eyebrow Lift” then the outcome of the subject is set to “no lift” for all analyses.
- If the result of one evaluator is missing and the other two evaluators disagree, then the outcome of the subject will be set to missing.

For treated subjects with missing outcome, the multiple imputation technique will be employed as described above for the primary and secondary analyses. For the worst case analysis, these subjects will be analyzed as having “no lift”.

All other effectiveness data will be analyzed as observed with no imputation of missing values. The denominator for percentages will be all subjects in the respective analysis set or population (i.e., missing data for binary or categorical variables will be presented as a separate possible category ‘Missing’).

CCI

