#### **6.4.5 Pooling of Sites**

Analysis will be performed on pooled data across all investigational sites.

Treatment site will be used as explanatory variable for the multiple imputation model. In case it turns out that convergence of the model cannot be accomplished, the two smallest sites will be merged and a new model will be calculated. This process will be repeated until convergence is established. The pooled site will be coded as ‘0099999’.

CCI

CCI

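### The Day 180 photographic-lift imputation uses only site, age and BMI and leaves out the subject's own Day 90 lift result, an optional refinement of a secondary endpoint

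*SAP*

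**What the plan says.** For Day 180 photographic lift, SAP 6.1.2 specifies 50 imputations by a fully conditional logistic method that "will use the investigational site and the baseline characteristics age and BMI as informing variables". The methods and code are carried over from the primary endpoint, where missing Day 90 lift is "modelled via logistic regression based on input variables site, age and BMI at baseline" (SAP 6.1.1.1).

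The other SAP sections add no predictor. SAP 6.4.1 refers back: "For treated subjects with missing outcome, the multiple imputation technique will be employed as described above for the primary and secondary analyses". SAP 6.4.5 deals only with sites: if the model does not converge, "the two smallest sites will be merged and a new model will be calculated". The SAS code is redacted, but the SAP prose names the variables, so this reading does not depend on hidden text.

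The Day 90 and Day 180 ratings are the same measurement at two times. SAP 2.1 states: "The same photographic assessment will be used for the secondary effectiveness endpoint with the comparator Photograph 2 collected at Day 180 post-treatment". Protocol 11.2.1.1.2 gives one question, one baseline photograph and one two-of-three rule for both visits. For the primary endpoint, "standardized 2D photographs will be taken at the screening visit and at Day 90, at a minimum" (Protocol 11.2.1.1). Stage 1 subjects enter the Day 180 analysis only if they reconsent, and that request is made at the Day 90 visit: "At Visit 3, Stage 1 subjects will be requested to reconsent for extended study participation to 180 days" (Protocol 11.1). Under Protocol 14.2.2 the database closes after Day 90 and again after Day 180.

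On sensitivity, SAP 6.1.2 says: "Sensitivity analyses and subgroup analyses will be performed similar to the primary endpoint". Under SAP 6.1.1.2 that means observed-case, worst-case and image-quality analyses.

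**The concern.** Multiple imputation removes bias only to the extent that the model's variables explain who is missing. The earlier rating of the same outcome is the obvious candidate predictor, and most subjects who miss Day 180 will have one. Without it, a Day 90 non-responder who is lost before Day 180 is imputed at roughly the rate seen in all observed subjects of similar site, age and BMI.

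If Day 90 non-responders are lost more often, the Day 180 proportion and its Wilson bound are too high. If responders are lost more often, they are too low. The planned sensitivity analyses do not settle this. The observed-case analysis carries the same bias, the worst-case analysis bounds the result from below only, and the image-quality analyses do not condition on Day 90 lift either.

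What is at stake is the blinded estimate of how well the lift lasts.

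**Working it through.** **The plan's own figure.** The documents give no figure for the Day 180 imputation. The nearest is the Day 90 sample size (SAP 3). With n = 40, a point estimate of at least 65% and a one-sided 95% Wilson lower bound above 50% require 26 responders (bound 52.0%). At 72% response the exact power is 87.6%, which agrees with the stated minimum of 85%.

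**Inputs from the documents.** Day 90 lift 72%; maximum attrition 10 of 50 = 20% (both SAP 3; I find no separate Day 180 allowance); up to five sites; 50 imputations. Only reconsenting Stage 1 subjects count at Day 180, so N is taken as 40 to 50.

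**Assumed inputs, not in the documents.** Day 180 lift a = 80% in Day 90 responders and b = 20% or 40% in the others; missing fractions d1 (responders) and d0 (others).

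**Large-sample bias of the plan's model.** If site, age and BMI carry no information, the model imputes at the observed rate:

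- True rate = 0.72a + 0.28b. This is 0.576 + 0.056 = 63.2% for b = 20%, and 0.576 + 0.112 = 68.8% for b = 40%.
- Estimate = [0.72(1 − d1)a + 0.28(1 − d0)b] / [0.72(1 − d1) + 0.28(1 − d0)].
- Example with d1 = 10%, d0 = 30%, b = 20%: (0.5184 + 0.0392) / (0.648 + 0.196) = 0.5576 / 0.844 = 66.1%, a bias of +2.9 points.
- Overall missing = 0.72 d1 + 0.28 d0.

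**Simulation.** 56 scenarios of 2,000 replicates; N = 40, 45 or 50; five sites with assumed shares of 30/25/20/15/10%; 50 imputations; 0% or 6% of subjects missing both visits. Sites are merged as in SAP 6.4.5. If the Day 90 model still cannot be fitted on one site, the plan's model is used. In 48 scenarios site, age and BMI are unrelated to lift; in 8 they are related. Bias is in percentage points, with Monte Carlo error of at most 0.11.

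| Dropout, responders/others | Overall missing (formula above) | Large-sample bias, b = 20% / 40% | Simulated bias, plan's model | Simulated bias, Day 90 lift added |
|---|---|---|---|---|
| 10%/10% | 10.0% | 0.0 / 0.0 | −0.4 to −0.1 | −0.4 to −0.1 |
| 5%/15% | 7.8% | +1.3 / +0.9 | +0.5 to +1.2 | −0.3 to +0.4 |
| 15%/5% | 12.2% | −1.4 / −0.9 | −1.8 to −1.2 | −0.8 to −0.4 |
| 10%/30% | 15.6% | +2.9 / +1.9 | +1.2 to +2.5 | −0.3 to +0.9 |
| 30%/10% | 24.4% | −3.2 / −2.1 | −3.9 to −2.6 | −1.9 to −0.9 |
| 10%/40% | 18.4% | +4.4 / +3.0 | +2.1 to +4.1 | −0.1 to +1.9 |

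Root-mean-square error, plan's model against the model with Day 90 lift: 2.3–3.5 against 2.1–3.3 at 10%/10%; 4.8–6.2 against 3.8–5.0 at 30%/10%; 4.3–5.9 against 3.6–4.7 at 10%/40%. For scale, the distance from the estimate to the one-sided Wilson bound is 11.5 to 13.0 points.

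**Fit failure.** The Day 90 model could not be fitted even with all sites merged in 7–30% of trials (b = 20%) or 1–11% (b = 40%), mainly because no observed Day 90 non-responder had Day 180 lift. Check at N = 40, 10%/40%, b = 20%: (1 − 0.28 × 0.6 × 0.2)^40 = 0.9664^40 = 25%, against 28% simulated. At least one site merge was needed in 33–75% of trials with the plan's model and 43–82% with the Day 90 term.

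**Weak link.** Same design at N = 45, nobody missing both visits, 1,500 replicates, Day 180 lift 75% against 60%. Root-mean-square error, plan's model against Day 90 added: 2.43 and 2.43 at 10%/10%; 2.12 and 2.21 at 5%/15%; 2.85 and 2.80 at 15%/5%; 3.11 and 3.27 at 10%/30%; 3.44 and 3.69 at 10%/40%. Bias went from +0.23 to −0.50 at 10%/30% and from +0.44 to −0.58 at 10%/40%.

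**The case against.** The plan's choice is defensible. It uses one baseline-only model at both visits, in a sample of about 40 to 50 for which the SAP already foresees convergence trouble. Nothing in the documents says that dropout depends on Day 90 lift, or how strongly the two visits are linked. With equal dropout the two models have the same bias. The larger biases need missingness near the planned maximum (18.4% for 10%/40%) or above it (24.4% for 30%/10%); at 5%/15% the bias is about 1 point.

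The remedy also has limits. It fails to fit most often where the link is strongest, so the choice of model then depends on the data and some bias remains, up to 1.9 points. The failure rates depend on the non-convergence rule used in the simulation (coefficient above 7 or variance above 50). The remedy does not restore information for a Stage 2 subject lost before Day 90 or a subject whose baseline photograph is unassessable. Day 90 results may also be known when the model is changed.

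All of this stands, and it limits the weight of the point. It does not remove it, because the omitted variable is already collected and closely matched to the outcome.

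A reader might infer that adding Day 90 lift can never do harm. In the 56 strong-link scenarios error fell or was unchanged, but with a 75%/60% link it rose by about 0.1 to 0.3 points in three of the five dropout patterns.

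**Conclusion.** The point holds as an optional refinement. The plan's Day 180 model omits the most relevant available predictor. With an assumed link of 80% against 20–40%, and missingness that depends on Day 90 lift, the Day 180 proportion moves by about 1 to 4 points, up or down. The upper end needs missingness near or above 20%. If missingness is unrelated to Day 90 lift, there is no material bias and only some loss of precision. More extreme assumptions give more: 90% against 10% lift with 10%/45% missing gives 74.6% against a true 67.6%, or +7.0 points. The documents offer no support for values that extreme.

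A reader might infer that the Day 180 result will be overstated, or that a success claim is at risk. The documents support neither. They give no direction for the dropout, and the readable text sets no threshold for Day 180 photographic lift. The Wilson success rule in SAP 6.1.2 belongs to the 0.5 mm quantitative endpoint, which is analysed on observed cases and does not use this model. The Day 90 primary analysis is unaffected.

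**What to change.** In SAP 6.1.2, add Day 90 lift as a predictor in the Day 180 FCS LOGISTIC model. In the same run, impute Day 90 lift jointly where it is missing, so that subjects missing both visits are covered. State that the Day 90 primary imputation remains a separate, unchanged run.

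Prespecify the fallback: if the model still does not converge after the site merging of SAP 6.4.5, drop the Day 90 term and report that this was done. Site merging cannot cure the main cause of failure, so the fallback is needed.

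Date the change before Day 180 ratings are available. Protocol 13 allows an SAP update before the final database close.

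The cost is one covariate and about two SAP sentences. In exchange the sponsor accepts one more parameter, more site merging, a fallback in about 1% to 30% of simulated trials, and a small rise in error in some dropout patterns if the Day 90 and Day 180 results turn out to be weakly linked.
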